## **7.5 SERIOUS ADVERSE EVENT REPORTING BY THE INVESTIGATOR**

### **Serious Adverse Event Reporting**

It is the responsibility of the Investigators or their designees to report any event of this nature to the sponsor or a designee within 24 hours of the event being brought to the Investigators' or their staffs' attention. It is also the responsibility of the Investigator to report all SAEs reported at their site to their Institutional Review Board (IRB), as required. The Investigator should make every attempt to follow all SAEs to resolution.

The following information should be provided when an SAE is reported to the sponsor or designee:

1. Protocol Number
1. Site Number
2. Subject Number
3. Subject Demographic information, including:
  - Date of Birth
  - Sex
  - Race
4. Investigational product start date
5. Date of last dose of investigational product
6. Date investigational product reinitiated (if investigational product interrupted)
7. SAE information, including:
  - SAE term (diagnosis only; if known or serious signs/symptoms)
  - Description of SAE/narrative
  - Date/time of onset
  - Severity
  - Outcome
  - Date/time of resolution or death (if duration < 24 hours)

- Relationship to investigational product
- Action taken with investigational product

8. Criteria for classifying the event as serious, including whether the SAE:

- Resulted in death.
- Was life-threatening
- Required inpatient hospitalization.
- Prolonged inpatient hospitalization.
- Resulted in a persistent or significant incapacity or substantial disruption of the ability to conduct normal life functions.
- Was a congenital anomaly/birth defect
- Important medical events that may not result in death, were not life-threatening, or did not require hospitalization may be considered serious when, based upon appropriate medical judgment, they may jeopardize the patient or subject and may require medical or surgical intervention to prevent one of the outcomes listed in this definition. Examples of such medical events include allergic bronchospasm requiring intensive treatment in an emergency room or at home, blood dyscrasias or convulsions that do not result in inpatient hospitalization, or the development of drug dependency or drug abuse.

9. Concomitant medications

10. Relevant history

11. Possible causes of SAE other than investigational product

12. Copy of AE page from the CRF

**NOTE:** If an SAE occurs in any study involving TRS01 that is unexpected and is determined to be related or possibly related to investigational product, all sites will be notified by the sponsor and each site should report it to its IRB.

## 8 EXPLORATORY EFFICACY

Measures of efficacy will be based on Investigator assessments of ACC and flare. At select sites, anterior chamber SD-OCT automated quantification of anterior chamber cells may also be used as a secondary measure of anterior chamber inflammation [Sharma et al., 2015].

### 8.1 EFFICACY VARIABLES

Efficacy of TRS01 will be assessed by evaluation of anterior chamber inflammation by Investigator assessment with slit-lamp biomicroscopy, and may also be assessed by anterior chamber SD-OCT automated quantification of anterior chamber cells at select sites.

Slit-lamp biomicroscopy of both eyes will be used to examine eye structures at each study visit. At Day1/Visit 1 (Screening/Randomization), slit-lamp biomicroscopy will be performed prior to IP administration. Areas assessed will include lids/lashes, conjunctiva, cornea, anterior chamber cells and flare, iris, pupil, lens.

#### 8.1.1 Anterior Chamber Cells

Note: The same investigator in each site must assess and score anterior chamber cells and flare across all study visits for an individual subject.

##### 8.1.1.1 Slit-lamp biomicroscopy

At each visit, slit-lamp biomicroscopy (halogen illumination system is required) will be performed by the Investigator on both eyes to assess ACC.

The following scoring scale for anterior chamber cells will be used:

##### 8.1.1.2 Spectral- Domain Optical Coherence Tomography

Anterior chamber SD-OCT imaging will be performed for the study eye on Visit 1/Day 1 after randomization (before first drop administration) and at each subsequent study visit, at select sites. [REDACTED]

#### 8.1.2 Flare

The level of flare in the anterior chamber will be assessed by the Investigator at each study visit for both eyes, using slit-lamp biomicroscopy and recorded according to the following scale:

- [REDACTED]
- [REDACTED]

- [REDACTED]
- [REDACTED]
- [REDACTED]

### **8.1.3 Macular OCT**

Both the average center subfield thickness and the macular volume will be evaluated on site by the investigator. Macular OCT will be performed for the study eye at Visit 1, Visit 5 and Visit 7 at select sites. Macular OCT should also be performed for the study eye at the visit where a subject is placed on rescue therapy.

### **8.1.4 Best Corrected Visual Acuity**

BCVA will be assessed using Early Treatment Diabetic Retinopathy Study (ETDRS) charts either retro-illuminated or frontally illuminated at a distance of 4 meters. Visual acuity will be measured with spectacle or pinhole correction at all study visits. The BCVA score and Snellen equivalent will both be recorded.

### **8.1.5 Subject-Rated Ocular Pain Assessment**

In the clinic, subjects will be handed a laminated card on which is printed the Subject-Rated Ocular Pain Assessment. Each subject will be asked to subjectively rate their pain at every visit based on this scale. This information will be provided to study personnel to enter into the subject's source documentation.

The grading scale for pain to be used will be as follows:

- 0 = None: Absence of pain.
- 1 = Minimal: Presence of mild sensation or discomfort (e.g., diffuse or focal foreign body sensation, mild transient burning or stinging, etc.)
- 2 = Mild: Mild, tolerable aching of the eye.
- 3 = Moderate: Moderate or more prolonged aching sufficient to have desire to use over the counter (OTC) analgesics (e.g. acetaminophen).
- 4 = Moderately Severe: More prolonged aching requiring the use of an OTC analgesic other than acetaminophen.
- 5 = Severe: Aching or throbbing pain that is not tolerable (e.g. constant or nearly constant sharp stabbing pain, throbbing or aching, etc.) requiring prescription analgesics.

## 9 STATISTICS

### 9.1 STATISTICAL METHODS

Continuous measures (e.g., age) will be summarized descriptively by the mean, standard deviation, median, minimum and maximum values. Categorical measures will be summarized by the number and percent of subjects. The statistical analyses will be performed in accordance with the Statistical Analysis Plan. All study data will be listed by treatment, subject and visit (as applicable).

#### 9.1.1 Subject Disposition, Demographic and Background Characteristics

Subject disposition, demographic characteristics, iris color, and background variables will be summarized by treatment group.

#### 9.1.2 Analysis of Safety

Analysis of safety data will be presented for all subjects. AEs will be coded using Medical Dictionary for Regulatory Activities (MedDRA, most current version add in version once finalized) and categorized by system organ class using preferred terms. Treatment emergent AEs will be listed by study group. Treatment related AEs will be tabulated by study group and will be reported by incidence (both number of events and number of subjects) with respect to their intensity and relationship to the IP. Ophthalmoscopy findings will be summarized descriptively. IOP measurements, VA, and slit-lamp biomicroscopy assessments will be summarized as safety outcomes.

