**Investigator Name:**

**Investigator's Signature:**

**Date**

**SYNOPSIS**

Sponsor	Tarsius Pharma, Ltd.
Study Title	A Phase I/IIa randomized, double masked, dose-ranging study to evaluate the safety and tolerability of TRS01 eye drops in subjects with active non-infectious anterior uveitis.
Study Objective	The primary objective of the study is to investigate the safety and tolerability of TRS01 [REDACTED] and [REDACTED] (w/v) eye drops in subjects with active non-infectious anterior uveitis.
Study Population	The study population will consist of male and female subjects, aged 18 or older, with active non-infectious anterior uveitis requiring initiation of additional topical steroid treatment.
Number of Subjects	Up to 20 subjects that meet the selection criteria will be randomized for treatment in one study eye.
Study eye	The study eye will be identified based on the severity of Anterior Chamber Cells (ACC) at Day 1. The eye with the most severe inflammation (higher ACC grade) will be selected as the study eye. If the ACC score is the same in both eyes, the right eye (OD) will be identified as the study eye. If the fellow eye has concurrent active uveitis at Day 1 or at any time during the study, the investigator can treat the subject's fellow eye per the standard of care. Only the study eye of each subject will be treated with IP.
Investigational Product	TRS01 [REDACTED] and [REDACTED] eye drops will be supplied as investigational product (IP).
Route and duration of administration	Study subjects will administer the randomly assigned treatment four times a day (QID) for 4 weeks.
Study Design	
This is a Phase I/IIa randomized, double masked, dose-ranging study designed to evaluate the safety and tolerability of TRS01 eye drops ([REDACTED] in subjects with active non-infectious anterior uveitis).
 
Potential study participants will be required to sign an informed consent document and meet all inclusion/exclusion criteria.
 
Eligible subjects will be randomized to treatment as follows:
 
 
[REDACTED]
 
 
Once it is determined that all eligibility criteria have been met, subjects will be enrolled and treated with one of two concentrations of TRS01 in a 1:1 ratio. Up to 20 eligible subjects will be enrolled at approximately

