#### 3.1 SAFETY ENDPOINTS

The primary safety parameter in this study is the incidence and severity of treatment-emergent and treatment-related adverse events (AEs), both systemic and ocular adverse events in subjects with inflammation due to active non-infectious anterior uveitis.

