7. Visit 7/Week 10 – Evaluation and study completion.

Please note that both eyes cannot be part of the study – there should be a treated eye (study eye) and an untreated eye (non-study eye).

A schematic of the study design is below in Figure 1: Study Schematic.

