## 7 SAFETY AND EFFICACY VARIABLES

### 7.1 SAFETY VARIABLE

Incidence and severity of treatment-related AEs and SAEs, both systemic and ocular reported adverse events.

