### 7.2.1 Adverse Events

Adverse events will be collected for subjects following signing of the ICF through the end of the study. The information will include at least a description of the event, onset date, and resolution date, as well as seriousness, severity and relation to study medication (as determined by the Investigator), location (right eye [OD], left eye [OS], both eyes [OU] or other), action taken, and outcome. All AEs will be coded using the Medical Dictionary for Regulatory Activities (MedDRA) dictionary, current version. Ocular and non-ocular AEs will be summarized separately.

*Suspected adverse reactions* (SARs), also known as adverse drug reactions or suspected adverse drug reactions, are AEs considered by the Investigator to be related to the study medication and included in the Investigator's Brochure.

An AE will be considered as an *ocular AE* if the Investigator selects 'OD', 'OS', or 'OU' for the AE eCRF field "Eye(s) affected".

Any AE that causes loss of vision of 15 or more letters (i.e., 3 lines) should be recorded as a serious adverse event (SAE). Examples include endophthalmitis, retinal vascular occlusion, retinal detachment involving the macula/fovea, etc. AEs that cause loss of 15 or more letters (i.e., 3 lines) that are expected to resolve should not be recorded as an SAE. Examples include corneal edema, corneal abrasion, cystoid macular edema or other conditions that are known to affect vision but expected to resolve and not result in a permanent impact on vision.

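### The primary safety parameter includes treatment-emergent AEs, but incidence by severity is tabulated only for related AEs, and the ocular AE category mixes dosed and undosed eyes

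*Combined protocol and SAP*

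**What the plan says.** Section 3.1 sets the primary parameter: "The primary safety parameter in this study is the incidence and severity of treatment-emergent and treatment-related adverse events (AEs"), covering systemic and ocular events. Section 7.1 is narrower: "Incidence and severity of treatment-related AEs and SAEs, both systemic and ocular reported adverse events".

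Section 9.1.2 states the outputs: "Treatment emergent AEs will be listed by study group. Treatment related AEs will be tabulated by study group and will be reported by incidence". The sentence goes on to require both event and subject counts, by intensity and relationship, but only for the related AEs.

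Section 7.2.1 adds that "Ocular and non-ocular AEs will be summarized separately". It treats an AE as ocular "if the Investigator selects 'OD', 'OS', or 'OU' for the AE eCRF field" recording the affected eye. The fields collected for each AE include severity, relationship and "location (right eye [OD], left eye [OS], both eyes [OU] or other").

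On dosing, the synopsis states that "Only the study eye of each subject will be treated with IP", and section 3.3 that "there should be a treated eye (study eye) and an untreated eye (non-study eye"). Section 9.1 defers the analyses to a Statistical Analysis Plan whose separate text is not in the document reviewed.

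**The concern.** In a safety and tolerability trial, the primary parameter should have a prespecified summary that matches it. Here treatment-emergent AEs get a listing, and the one table of incidence by intensity is restricted to events the investigator judged related.

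That restriction matters in this design. Both arms receive TRS01, so there is no untreated arm against which to check attribution. Section 7.3 classes an event that uveitis readily accounts for as unrelated, and its causality scale has no level between unrelated and probable. Section 1 names pain, blurred vision and conjunctival hyperemia among the manifestations of uveitis. These are also the kinds of event that poor tolerability of an eye drop could produce, so such events may never reach the table.

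The second problem is the ocular category. The fellow eye receives no study drug and may be given standard-of-care treatment, yet its AEs fall into the same category as those of the dosed eye. An ocular AE incidence built on that definition does not describe tolerability in the treated eye.

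**Working it through.** The plan gives no figure to reproduce: section 9.2 reports no formal sample size estimation and no AE rate is stated. The check is a comparison of the text, followed by simple arithmetic.

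**Parameter against outputs**

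| Section | Events covered | What is promised |
|---|---|---|
| 3.1 | Treatment-emergent and treatment-related, systemic and ocular | Incidence and severity, as the primary parameter |
| 7.1 | Treatment-related AEs and SAEs | Incidence and severity |
| 7.2.1 | Ocular and non-ocular AEs | Separate summaries; no severity split, no restriction to treatment-emergent events, no study-eye split |
| 9.1 | Any categorical measure | Number and percent of subjects; all data listed |
| 9.1.2 | Treatment-emergent | Listing by group |
| 9.1.2 | Treatment-related | Table of events and subjects by intensity and relationship |

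No row gives treatment-emergent incidence by severity, and none gives ocular AEs by study eye. Since section 9.1 already lists all data by treatment and subject, the listing of treatment-emergent AEs adds little to that default.

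**Which reading of 3.1?** It can mean two sets of events, or only those that are both emergent and related. Under section 7.3 an event before dosing is unrelated, so a related event already begins after dosing. On the usual meaning of treatment-emergent, which the available text does not define, the second reading makes that word redundant. The two-set reading is the more natural one, but the text does not settle it.

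**Fellow-eye events are collected.** Section 5.1.1 has AEs assessed in both eyes after the first dose, and section 7.2.1 records location as right, left, both or other.

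**Size of the units** (section 9.2: up to 20 subjects; section 3.3: 1:1 allocation)

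- Subjects per arm: 20 / 2 = up to 10.
- One subject: 1/10 = 10 percentage points of incidence in an arm, 1/20 = 5 points overall.
- Eyes: 20 × 2 = up to 40, of which 20 are dosed and 20 are not; 20/40 = 50% of the eyes able to yield an ocular AE receive no study drug.

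**Illustration on assumed rates only.** None of these rates is in the documents.

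- If 30% of subjects in an arm of 10 have a treatment-emergent AE (3 expected) and 25% to 75% of those have one called related, the related table shows 0.75 to 2.25 of the 3. At 50% (5 expected) it shows 1.25 to 3.75 of the 5.
- With a study-eye AE rate of 20% and an independent fellow-eye rate f, the either-eye rate is 1 − (1 − 0.20)(1 − f): 20% at f = 0, 28% at f = 10%, 36% at f = 20%.

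**The case against.** Section 7.1 points towards a parameter restricted to related AEs. If that is what 3.1 means, the table in 9.1.2 fits and only the wording is at fault. Section 7.2.1 together with 9.1 would already give number and percent of subjects for all AEs. Consent, randomization and first dose all fall at Visit 1, so all AEs and treatment-emergent AEs should differ little. The right/left/both rule serves to separate ocular from non-ocular events and does not itself prescribe pooled tables. An event confined to an undosed eye would usually be called unrelated and so stay out of the related-AE table. The arithmetic above holds for any one-eye design with 10 per arm. Finally, AE table layouts commonly sit in the SAP, which is not available here.

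Much of this stands as a limit. The listing permits a hand count. Several measures are free of attribution: pain is rated 0 to 5 at every visit and compared by arm at Weeks 1 to 4, conjunctival hyperemia is graded 0 to 3 at all visits, and BCVA and IOP are measured at all visits. The fellow-eye problem mainly affects the 7.2.1 summary.

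The central point remains. The 7.2.1 summary has no severity split, although severity is half of the primary parameter. The attribution-free measures are all ocular, are taken at visits, and are not AE incidence, whereas 3.1 also covers systemic events. Attribution may keep fellow-eye events out of the related-AE table, but it does nothing for the ocular category in 7.2.1.

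**Conclusion.** The concern holds and should be fixed. Followed as written, the available text does not produce the incidence and severity of treatment-emergent AEs that 3.1 makes primary, and its ocular AE category does not distinguish the dosed eye from the undosed one. Sections 3.1, 7.1 and 9.1.2 do not describe the same parameter.

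No bias can be quantified from the documents, and no data are lost. The conclusion rests on the two-set reading of 3.1; on the narrower reading, what remains of the first part is ambiguous wording in 3.1, and the eye-pooling part is unaffected. It is confined to the text available, since the separate SAP may contain the missing tables.

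**What to change.** - In 9.1.2, tabulate all treatment-emergent AEs, as numbers of subjects and of events, by system organ class, preferred term and maximum severity, by arm and overall. Show related AEs as a subset.
- Present ocular AEs separately for the study eye and the fellow eye, derived from the recorded location, with an event in both eyes counted under each.
- State in 3.1 that treatment-emergent and treatment-related AEs are two sets, if that is the intent, and bring 7.1 and 7.2.1 into line.
- If the SAP already specifies these tables, refer to them in 9.1.2.

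The cost is table programming and wording. Severity, relationship and location are already collected for every AE, so no new data or assessments are needed.

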#### 9.1.3 Analysis of Efficacy

Efficacy measures will be ACC and flare.

Both Investigator-rated ACC and flare data will be assessed as a change from baseline (Visit 1/Day 1) Weeks 1 through 4 and a descriptive comparison of the two active treatment groups will be performed.

If available, anterior chamber SD-OCT cell data will be assessed as a change from baseline (Visit 1/Day 1) on Weeks 1 through 4 and a descriptive comparison of the two active treatment groups will be performed.

Changes in subject-rated ocular pain assessment on Weeks 1 through 4 will be evaluated via a descriptive comparison between the two active treatment groups.

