### 6.2 PERMITTED MEDICATIONS

Subjects on therapy for their uveitis will not be asked to stop their usual medications, rather they will add TRS01 QID to their current regimen. Therapy considered necessary for the subject's welfare that does not interfere with the evaluation of the study medication will be permitted to be given at the discretion of the Principal Investigator.

The decision to administer a prohibited medication or treatment would be taken with the safety of the subject as the primary consideration. Whenever possible, the Tarsius Medical Director will be notified before any prohibited medications or treatments are administered. The Tarsius Medical Monitor should also be contacted if the permissibility of a specific medication or treatment is in question.

Any subject placed on rescue therapy will discontinue use of the IP and continue study participation through Visit 7.

Subjects on rescue therapy due to lack of efficacy should not be withdrawn from the study, but rather followed through the end of the study.

Rescued subjects experiencing an AE at the time of rescue will be followed through stabilization or resolution of the AE or the end of the study (whichever comes first).

The following medications are also specifically permitted during the trial:

- Glaucoma eye drops with the exclusion of Prostaglandins. Note: subjects may be treated with up to two glaucoma eye drops in the study eye. Anti-glaucoma eye drops should be [REDACTED] before the investigational product dosing.
- Mydriatic agents
- Use of PRN artificial tears up to twice a day
- [REDACTED]  
[REDACTED]

- [REDACTED]
- [REDACTED]
- [REDACTED]
- [REDACTED]

**The above medications, if used at the onset of the trial, must not be discontinued during the course of the trial and the dosing and regimen should remain stable through Visit 5 (end of IP treatment period).**

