**TABLE 3: OCULAR SAFETY MEASURES**

Safety Measure	Note
Slit-lamp biomicroscopy: Lid hyperemia, lid edema, conjunctival hyperemia, chemosis, corneal edema, conjunctival discharge/exudate	The status of each of these biomicroscopy parameters will be rated as 0 = None, 1 = Mild, 2 = Moderate, or 3 = Severe. For each abnormal record, the clinical significance (Clinically Significant or Not Clinically Significant) will also be determined. Slit-lamp biomicroscopy will be performed at all study visits.
Intraocular pressure	The IOP measurements will be performed by Goldmann applanation tonometry with a single measurement. IOP pressure recorded in mmHg (e.g., 18 mmHg). IOP measurements will be performed at all study visits,
Dilated Ophthalmoscopy: Vitreous haze, retina vessels, macula, optic nerve, cup/disc ratio.	The status of the macula, vessels and optic nerve will be determined as Normal or Abnormal. The cup/disc ratio will be recorded with two decimal points (e.g., 0.80). Dilated ophthalmoscopy will be performed at all visits.
BCVA	The visual acuity test is used via a standardized ETDRS chart.

These ocular safety measures will be summarized using descriptive statistics. For continuous ocular safety measures, changes from Baseline (Day 1/Visit 1) variables will also be summarized descriptively. Safety parameters of interest include a change from baseline to each visit in ocular signs such as corneal/conjunctival tolerability, IOP measurements.

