### 7.2.2 Criteria for Rescue Therapy

Rescue therapy will be offered if one or more of the following rescue criteria are met and a rescue therapy treatment plan is discussed with the Tarsius Medical Officer:

- If visual acuity in the study eye decreases by >2 lines compared to baseline, which in the opinion of the investigator, is due to non-infectious anterior uveitis.
- [REDACTED]

If rescue therapy is initiated, the subject will be instructed to discontinue IP. The choice of rescue therapy will be at the discretion of the Investigator. If rescue therapy is administered, the generic name, indication, route of administration, frequency, dose, start date, and stop date (if applicable) will be recorded on the eCRF. In addition, if other local therapy (i.e., periocular or intravitreal corticosteroids) is administered in the non-study eye, then the generic name,

indication, route of administration, frequency, dose, start date and end date (if applicable) would also be recorded on the eCRF.

Any medication administered on Visit 5 (Day 28) after the subject has exited the study will not be considered as rescue therapy.

If possible, during the visit where rescue therapy is initiated, Macular OCT should be performed for the study eye.

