## **9.4 PROCEDURE FOR ACCOUNTING FOR MISSING, UNUSED, OR SPURIOUS DATA**

Any missing, unused, or spurious data will be noted in the final clinical study report.

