## **9.6 SUBJECTS TO BE INCLUDED IN THE ANALYSIS**

Intent-to-Treat (ITT) Population: The ITT population will include all randomized subjects who took at least 1 dose of investigational product. The Safety Population will include all randomized subjects.

Per Protocol (PP) Population: The PP population is a subset of the ITT population, which will include those subjects who did not have significant protocol deviations. The PP population will be defined and documented by the clinical study team and the biostatistician prior to database lock and unmasking of the subjects.

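### The visible summaries of ACC, flare, pain and IOP do not separate values recorded after rescue, when IP has stopped but study visits continue

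*Combined protocol and SAP*

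**What the plan says.** On efficacy, Section 9.1.3 states: "Both Investigator-rated ACC and flare data will be assessed as a change from baseline (Visit 1/Day 1) Weeks 1 through 4", followed by a descriptive comparison of the two dose groups. For pain: "Changes in subject-rated ocular pain assessment on Weeks 1 through 4 will be evaluated via a descriptive comparison between the two active treatment groups".

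On IOP, the text under Table 3 states: "Safety parameters of interest include a change from baseline to each visit in ocular signs such as corneal/conjunctival tolerability, IOP measurements". Section 9.1.2 adds: "IOP measurements, VA, and slit-lamp biomicroscopy assessments will be summarized as safety outcomes".

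On rescue, Section 6.2 states: "Any subject placed on rescue therapy will discontinue use of the IP and continue study participation through Visit 7". Section 7.2.2 repeats the stop: "If rescue therapy is initiated, the subject will be instructed to discontinue IP". Section 6.2 also keeps subjects rescued for lack of efficacy under follow-up to the end of the study. Section 6.3 defines rescue by what the treatment does, whatever the reason for giving it and whatever label it carries on the eCRF.

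On data handling, Section 9.4 states: "Any missing, unused, or spurious data will be noted in the final clinical study report". Section 9.6 limits the Per Protocol set to "those subjects who did not have significant protocol deviations". Section 9.1 refers the analyses to a Statistical Analysis Plan, whose text is not in the supplied document, and says that all data will be listed by treatment, subject and visit.

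**The concern.** The protocol deliberately goes on collecting ACC, flare, pain and IOP from subjects who have stopped TRS01 and started another anti-inflammatory treatment. The visible summaries then report those measurements by assigned dose, with no mark at the point where treatment changed.

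Both arms receive TRS01, so any impression of activity comes from change within an arm. If a subject worsens on TRS01, is rescued at Week 1 and improves on steroid, the Week 2 to 4 values enter the arm's mean as improvement. A treatment failure then looks like a response.

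IOP can be misread in the other direction. Section 1 names raised IOP among the most common adverse effects of ocular steroids. A rise caused by a rescue steroid would appear in the TRS01 safety table, and the case for TRS01 in Section 1 is the need for a drug that does not raise IOP.

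**Working it through.** The documents give no power, effect size, SD or rescue rate, so there is no stated figure to reproduce. The check has four steps.

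**1. Does any visible rule cover post-rescue values?**

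| Section | What it covers | Does it separate post-rescue values? |
|---|---|---|
| 9.1.3 | ACC, flare, pain, Weeks 1 to 4 | No mention of rescue |
| Table 3 text, 9.1.2 | IOP, including change to each visit | No mention of rescue |
| 9.4 | Missing, unused or spurious data | No: a post-rescue value is none of these, and the action is only to note it |
| 9.6 | Per Protocol set | No: it removes whole subjects for deviations, rescue is a step the protocol provides for, and no analysis is assigned to the set |
| 6.3 | Definition of rescue | It could drive a derived classification, but no visible analysis uses one |

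**2. Size at a single visit.** Inputs: up to 20 subjects (Section 9.2) and 1:1 allocation (Section 3.3), so 20/2 = 10 per arm. With k rescued subjects in an arm and a difference d made by rescue treatment:

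- share of the arm at each later visit = k/10, so 10%, 20% and 30% for k = 1, 2 and 3;
- shift in the arm mean = k × d/10.

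The values of d are assumptions, since the documents give none and the ACC scale is not legible.

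| | k = 1 | k = 3 |
|---|---|---|
| ACC, d = 1 to 2 grades | 0.1 to 0.2 grade | 0.3 to 0.6 grade |
| IOP, d = 5 to 10 mmHg | 0.5 to 1.0 mmHg | 1.5 to 3.0 mmHg |

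**3. Which alternative summary shows failures as failures?** Assume that non-rescued subjects change by -1 ACC grade, and that rescued subjects stand at +1 when rescue starts and at -2 afterwards. Let one subject be rescued in arm A and four in arm B.

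- All values: A = (9 × -1 + 1 × -2)/10 = -1.1; B = (6 × -1 + 4 × -2)/10 = -1.4. B looks 0.3 grade better.
- Post-rescue values deleted: A = -9/9 = -1.0; B = -6/6 = -1.0. The failures vanish from the mean.
- Last value at or before rescue carried forward: A = (9 × -1 + 1 × 1)/10 = -0.8; B = (6 × -1 + 4 × 1)/10 = -0.2. B is 0.6 grade worse.

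The case is chosen to show the mechanism. It is not a prediction. It shows that deletion is the wrong remedy and that carrying the pre-rescue value forward keeps the failure visible.

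**4. Is rescue likely enough to matter?** Entry requires disease that calls for starting or increasing topical steroid (Section 4.1), while Section 5.1.1 asks for stable background dosing during IP treatment. For an assumed true rescue rate p:

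- the chance of at least one rescue among 20 is 1 - (1 - p)^20, which is 88% at p = 10% and 99% at p = 20%;
- with the same p in both arms, the chance that two independent binomial counts of 10 differ by two or more is 24% at 10%, 39% at 20%, 46% at 30% and 49% at 40%.

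**The case against.** The strongest reply is that Section 9.1 sends the analyses to a separate SAP, which is where a rule on rescue would normally sit. Its absence from a short protocol section does not show that no rule exists. This stands, and it limits the point to the visible text.

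Second, efficacy is exploratory and descriptive. Rescue drug, dose and dates are recorded (Section 7.2.2), all data are listed, and with about 10 subjects per arm a careful reader could find the affected values. This also stands, but a listing does not correct a summary table, and a separation first chosen after unmasking can be chosen by its result.

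Third, the primary safety parameter is adverse events (Section 3.1), which carry an investigator's judgement of relatedness, so a steroid-related IOP event can be classed there as unrelated. That is true of events. The IOP summaries carry no such judgement.

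Fourth, with no vehicle and with background therapy allowed, within-arm change cannot establish activity even after this repair. This is correct. The repair removes one misleading element and does not supply a control.

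A reader might also infer that a study-eye steroid started or raised within twice-daily dosing escapes the rescue definition in Section 6.3. The documents do not support that. Parts of Sections 6.2 and 7.2.2 that may settle it are redacted, and Section 5.1.1 visibly asks for stable dosing, with cycloplegics as the exception.

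**Conclusion.** The concern holds for the visible text and is a cheap improvement. Followed as written, the plan lets values recorded after rescue count towards the assigned TRS01 dose for ACC, flare, pain and IOP. Each rescued subject is 10% of an arm of 10 at every later visit. Under the assumed effects, that is 0.1 to 0.2 ACC grade or 0.5 to 1.0 mmHg in the arm mean per subject. The IOP figure also assumes that the rescue treatment is one that raises IOP.

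Two stronger conclusions might be drawn, and neither is supported. One is that the comparison between doses is biased. That requires rescue, or its effect, to differ between arms; such a difference can arise by chance, but none is documented. The other is that the trial's main result is invalid. The primary parameter is adverse events, and no formal test depends on these summaries. What is affected is how the descriptive tables are read. The efficacy summaries end at Week 4, so Weeks 7 and 10 matter here only for IOP, and by then every subject is off IP by schedule.

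**What to change.** Add the following to Sections 9.1.2 and 9.1.3, or to the SAP, before unmasking:

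- Rescue, and its start date, will be derived from the concomitant-medication data using the Section 6.3 definition, whatever the eCRF label. For this purpose, analgesics, changes in cycloplegics and treatment of the fellow eye only do not count as rescue.
- Study-eye ACC, flare and pain at Weeks 1 to 4 will be summarised with all values and, side by side, with the last value at or before the start of rescue used for all later visits.
- Study-eye IOP will be summarised with all values and also separately for values before and after the start of rescue.
- The number of rescued subjects will be reported by arm and visit.

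The analgesic exclusion matters because the upper pain grades in Section 8.1.5 are themselves defined by analgesic use. If the SAP already holds an equivalent rule, a pointer to it in Section 9.1 is enough.

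The cost is one derived date and one extra set of summary columns. A treated-eye field is also needed if the eCRF lacks one, since the medication fields listed in Section 6.1 do not include the eye. Sample size, visits and treatment do not change. The apparent response may look less favourable. The carried-forward value is itself an assumption about what would have followed without rescue, so that summary belongs beside the all-values summary and should not replace it.
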